 N/A, there is no direct benefit. However, subjects may experience decreased levels of anxiety as a result of listening to music.
2. *Describe any benefit to the population from which the subject is drawn:*
If proven effective, music could be offered to more patients in the pre-operative setting to help reduce their levels of anxiety and could provide more accurate “dosing” estimates of music duration for clinicians to use.
3. *Describe any benefit to science, society, and humanity in general:*
The results of this study will help further reveal the effect characteristics of music on anxiety.

B.4 Alternatives

1. *Describe alternatives to participating in this research study (e.g. to decide not participate in the study, alternative treatments, no treatment (palliative care), etc.):*
The alternative is not participating in the study.
2. *Describe the standard clinical care that may be an alternative:* N/A
3. *Describe how the subject can receive the research procedures/drug/device used in this study in a non-research setting:* The subject may use their own music-playing devices if so desired

C. Objectives

1. *Describe the purpose, specific aims, or objectives of the study (i.e. the reason for performing the study in terms of the scientific question to be answered):*
The primary objective of this study is to determine effective dose of music duration for anxiety reduction in parturients awaiting non-emergent cesarean section.

A secondary objective of this study is to compare the effective dose of music duration for anxiety reduction between classical pieces previously studied vs. patient-preferred music selection.

An additional secondary objective is to analyze the physiologic impact from anxiety reduction pre- and post-study intervention.

An exploratory objective of this study is to investigate the dose-duration relationship of music on anxiety reduction in patients awaiting non-emergent cesarean section.

D. Enrollment and Withdrawal

D.1 Inclusion Criteria

1. *Describe the criteria that define who will be included in the study as a numbered list:*
 1. Age: 18 years old or older.
 2. Planning a scheduled or urgent (non-emergent, i.e. for arrest of labor) cesarean section.
 3. Able to provide informed consent.
 4. American Society of Anesthesiologists (ASA) physical status rating of II-III. (Mild systemic disease; severe systemic disease that is not incapacitating)

D.2 Exclusion Criteria

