- Once consent is given, the study subjects will be asked to assess their anxiety level on a scale of 0-10, 0 being no anxiety at all. Additionally, they will be asked to complete 6 STAI questionnaire prompts to further assess their anxiety levels. If the score is 0, they will automatically be removed from the study (as per the exclusion criteria). If the score is greater than 0, a baseline heart rate and blood pressure will be recorded, and the participant will proceed to the study intervention.
- All study participants will be also initially asked to choose four songs of personal preference that they would enjoy listening to. These song choices will be written down on their pre-intervention screening questionnaire and later used if their pre-determined music selection falls into the “personal preference” study arm.
- If there are multiple support people present in the room, the participant will be asked to identify a maximum of one person to stay in the room for the study intervention.
- The study intervention includes listening to pre-selected music, randomized to selections either from Conrad, et al. or from their own preference list, for a pre-determined duration ranging from 1-30 minutes. This intervention is being performed exclusively for research purposes and is not part of the standard of care. The study subjects will listen to this music played from a speaker connected to an audio device, both supplied by the research team. The investigator and patient will collaborate on patient positioning (supine, semi-recumbent, seated upright, etc.) to optimize patient comfort during the study intervention. Active participation on the study subjects’ part will be required to continually assess the volume of the music being played to avoid potential tympanic-membrane injury.

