- Once the music play duration has lapsed, the study subject will be asked to then reassess their anxiety level on the same 1-10 scale as pre-music intervention. This reassessment will be performed at three event points: directly following completion of music duration, just prior to transport to the OR, and directly upon arrival in the OR. STAI questionnaire completion will be assessed only directly following completion of the intervention, not before transport to the OR or upon arrival in the OR. Heart rate and blood pressure measurements will be recorded at all three post-intervention assessments. After completion of the final post-music assessment, this will conclude the study subject’s participation.
- Pre- and post-music anxiety scores will be recorded and correlated to the study subjects’ assigned 3-digit codes.
- Once all 30 (or 33 maximum) subjects in each intervention group have undergone the study protocol, their pre- and post-anxiety data will be analyzed.

Please also describe the following concerning procedures:

- a. *How individuals will be screened for eligibility. Specify screening that will take place prior to informed consent and screening that will take place after informed consent:*
Patients will be screened for eligibility by the PI or Co-I and will be required to meet all inclusion criteria and none of the exclusion criteria. To do this, a brief chart review will be performed to assess age and ASA clinical status, and to ensure that daily anxiolytic medications are not taken at baseline. After informed consent, the first 0-10 anxiety rating and STAI questionnaire will be completed by the participant. If their anxiety score is rated as 0, then at that time they will be excluded from participating in the study.
- b. *Procedures being performed to monitor subjects for safety or to minimize risks:*
As stated above, the PI or Co-I will remain nearby to continually assess volume status of the music to prevent potential tympanic membrane injury.
- c. *The source records that will be used to collect data about subjects. (Submit all surveys, scripts, and data collection forms.):*
See attached data collection and anxiety-screening forms

2. *Is there a placebo control arm?*
 Yes No
3. *Describe the following concerning pregnancy testing and birth control:*
 - a. *What type of pregnancy testing and how frequently will be conducted on women of reproductive potential. If testing will not be conducted provide the reason:*

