Pregnancy testing will not be conducted, as it would be redundant since only patients already admitted to the Tufts Medical Center Labor and Delivery Unit who are scheduled for cesarean section will be approached and recruited for this study.
 - b. *What birth control methods women of reproductive potential will be instructed to use. If women will not be instructed about acceptable methods of birth control, clarify why:*
Birth control methods will not be discussed as part of this study. These discussions will be left to be had between the patients and their OB/Gyn or primary care providers.
 - c. *What birth control methods men of reproductive potential will be instructed to use. If men will not be instructed about acceptable methods of birth control, clarify why:*
This study will only enroll participants of female sex. If female-sex-assigned-at-birth subjects identify their gender as male, their discussions surrounding birth control will be left to be had between them and their OB/Gyn or primary care providers.
4. *Describe the data that will be collected during the study and how the data will be obtained:*
The data collected during this study will include patient age, race, ethnicity, height, weight, gestational age, gestational history, ASA status, blood pressure and heart rate measurements, and cesarean delivery type (scheduled vs. unscheduled). This data will be obtained through a combination of chart review, oral history taking from the participant, and physical measurement (for blood pressure and heart rate) by the investigator. Anxiety ratings on a 0-10 scale and an STAI scale will also be collected by the investigator.
 - a. *If there are plans for long-term follow-up (once all research related procedures are complete), describe the data will be collected during this period:* N/A
5. *Specify which procedures, tests, visits, etc. described above are:*
 - a. *Part of usual standard of care at Tufts:*
Acquisition of heart rate and blood pressure measurements are part of the standard of care at Tufts Medical Center, as are the determinations of age, race, height, weight, ethnicity, gestational age, gestational history, and ASA status.
 - b. *Performed solely for research purposes:*
Anxiety ratings on the 0-10 scale and STAI scale will be performed solely for research purposes.

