Check to confirm that reportable new information will be reported to the IRB per the Tufts Health Sciences IRB's [Reportable New Information policy](#). If your reporting plan to the IRB differs from the IRB's policies, please describe it in detail or specify where this information is in the protocol:

I. Statistical Considerations

I.1 Study Endpoints

1. *Describe the primary and secondary study endpoints:*

Primary endpoint: determination of the 95th percentile effective dose of music duration for anxiety reduction.

Secondary endpoint: compare the 95th percentile effective dose of music duration for anxiety reduction between the Mozart and personal-preference intervention arms.

Secondary endpoint: analyze and compare pre-and post-intervention heart rate and blood pressure measurements.

Exploratory endpoint: analyze and compare anxiety ratings at the three post-intervention event-point measurements.

Exploratory endpoint: analyze and compare anxiety ratings using the 0-10 scale with the STAI questionnaire.

2. *Describe any primary or secondary safety endpoints:* N/A

I.2 Sample Size Justification Statistical Analyses

1. *Describe the statistical analyses that will be performed for this study:*

Statistical analysis to determine the ED₉₅ will be conducted using the methods described by Pace, Stylianou, and Warltier (8).

2. *Provide a sample size justification:*

The plan is to enroll up to 33 subjects per treatment group (up to 66 total), with a minimum goal of 30 per group (60 total). This is based on prior studies that suggest 20-40 study subjects are required for adequate statistical power in sequential allocation biased coin design studies, and we expect a ~10% attrition rate. A goal of 33 subjects per group will thus likely turn into an estimated sample size of 30 after attrition, which falls well within the acceptable sample size range.

I.3 Number of Subjects

1. *Specify the number of subjects to be enrolled in total across all sites:* N/A this is not a multicenter study.

2. *Specify the number of subjects to be enrolled at the Tufts site(s)¹. Subjects who sign an ICF are considered “enrolled”. For studies that have a separate screening ICF, this number is the number of subjects who sign a screening ICF:*

- a. *Specify the number of subjects expected to be enrolled at the Tufts site (i.e. sign the screening or study ICF):*

Up to 66 subjects.

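### Baseline heart rate and blood pressure precede the step in which posture is chosen, and posture is neither held constant nor listed as data, so the pre/post physiologic endpoint can mix postural change with anxiety reduction

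*Combined protocol and SAP*

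**What the plan says.** Section C sets a secondary objective to "analyze the physiologic impact from anxiety reduction pre- and post-study intervention". The matching secondary endpoint in I.1 is to "analyze and compare pre-and post-intervention heart rate and blood pressure measurements".

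F.2 item 1 gives the procedures in order:

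- **Baseline.** After the 0-10 score and the STAI prompts, if the score is above 0, "a baseline heart rate and blood pressure will be recorded, and the participant will proceed to the study intervention".
- **Intervention.** In the bullet on the music itself, investigator and woman "collaborate on patient positioning (supine, semi-recumbent, seated upright, etc.) to optimize patient comfort during the study intervention".
- **After the music.** "Heart rate and blood pressure measurements will be recorded at all three post-intervention assessments". These fall "directly following completion of music duration, just prior to transport to the OR, and directly upon arrival in the OR".

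F.2 item 4 describes the method only as "physical measurement (for blood pressure and heart rate) by the investigator". Its list of data has no entry for posture. Section L lets nursing help with vital signs within usual practice, and it too says nothing on posture. The statistical method in I.2 concerns the ED95 only; none is given for heart rate or blood pressure.

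**The concern.** The objective is causal: it attributes the pre/post change in heart rate and blood pressure to reduced anxiety. Both quantities also depend on posture. If a woman is measured in one posture at baseline and in another after the music, the difference contains a component that would be there without music or any change in anxiety.

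The design offers no way to take that component out. A line in B.1 speaks of a control equal to standard practice, but F.2, G.3 and I.5 describe two arms that both receive music. There is thus no music-free group in which to see the postural change alone. If posture is not recorded, no later analysis can separate it, and adjusting for the baseline value does not remove a change of posture between readings. Net movement in one direction would shift the mean. Movement in both directions would add scatter and could hide a real effect.

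**Working it through.** **1. Order of steps, from the text.** Baseline vital signs come before the participant proceeds to the intervention. Positioning is described within the intervention and tied to comfort during it. The first post-music reading follows directly. Baseline before choice of posture is therefore the natural reading of F.2, although no sentence says that posture changes after baseline.

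**2. Control of posture.** C, F.2 items 1, 4 and 5, I.1 and L are the places that mention heart rate, blood pressure, vital signs or positioning. None fixes a posture for a reading, asks for the baseline posture to be repeated, or lists posture as data.

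**3. Size.** The plan has no figure to reproduce: it gives no SD, effect size or alpha for these endpoints. What follows is illustration for blood pressure only.

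Inputs: n = 60, the completers in I.3 with arms pooled; SD of within-woman change 10 mmHg (assumed); no true effect of anxiety reduction; moves all in one direction (assumed).

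- SE = 10/√60 = 1.29 mmHg. The two-sided 5% cut-off for t with 59 df is about 2.00 SE.
- Net mean shift = fraction moving × shift per mover.

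| Fraction moving | Shift per mover (mmHg) | Mean shift (mmHg) | Mean shift / SE |
|---|---|---|---|
| 0.25 | 5 | 1.25 | 1.25/1.29 = 1.0 |
| 0.5 | 5 | 2.5 | 2.5/1.29 = 1.9 |
| 0.5 | 10 | 5.0 | 5.0/1.29 = 3.9 |

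The second row falls just short of the cut-off. In the third row, if 10 mmHg is the SD without posture, a shift in only half the women widens it to √(10² + 0.5 × 0.5 × 10²) = 11.2. The SE becomes 11.2/√60 = 1.44, and the ratio is 5.0/1.44 = 3.5.

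**4. Chance of a significant paired t-test** (two-sided 5%, noncentral t) when the only change is postural, for an assumed SD of change of 8 to 12 mmHg:

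| Net mean shift (mmHg) | n = 30 (one arm) | n = 60 (pooled) |
|---|---|---|
| 0 | 5% | 5% |
| 2 | 14-26% | 25-48% |
| 3 | 26-51% | 48-82% |
| 5 | 60-91% | 89-100% |

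**5. Moves in opposite directions.** If a quarter of women shift up by 10 mmHg and a quarter down by 10 mmHg, the mean shift is 0. The SD becomes √(10² + 0.5 × 10²) = 12.2, which is 22% wider. The result is lost precision without bias.

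**The case against.** The strongest case is that the text does not show what a reader might infer from it.

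- **That women are repositioned after baseline.** Bullet order alone is weak evidence: the song-choice bullet comes after the baseline bullet, yet that task is done at the start. A woman may keep the posture she already has. This stands, so the mixing is possible and uncontrolled, not certain in each woman.
- **That women sit for consent and then recline for the music, which would bias the mean one way.** No passage says so. G.5 allows the consent discussion at the bedside or in a private room, and F.2 item 3 describes women already admitted to the unit. No direction can be assumed.
- **That posture is not recorded at all.** F.2 refers to attached data forms that are not in the visible text. The list in F.2 item 4 is also incomplete, since song choices are collected but not listed there. The absence can be claimed only for the visible text.

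The consequence is also limited. Both arms follow the same positioning rule, so randomization balances posture between them in expectation. The ED95 does not use these readings. Fixing posture would not make the pre/post change attributable to anxiety reduction, because time, waiting and the approach of surgery remain in it.

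What survives is narrower. The stated sequence leaves open an avoidable source of bias and noise in a named secondary endpoint, and as far as the text shows it could not be examined afterwards.

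**Conclusion.** The point holds as a cheap improvement to a secondary endpoint. Because baseline vital signs come before posture is chosen, and posture is neither held constant nor visibly recorded, the within-woman change in heart rate and blood pressure can mix postural change with any effect of anxiety reduction. The arm comparison gains only noise.

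Size and direction cannot be had from the documents. Under the assumed SD and n, a net shift of 1.25 mmHg would matter little, 2.5 mmHg would be borderline, and 5 mmHg would nearly always give a significant result with no effect of music. These figures need a net movement in one direction, which the documents neither state nor exclude. A reader might go further and call the physiologic endpoint invalid, or expect a false positive. The documents support neither.

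**What to change.** In F.2:

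1. Let the woman settle in the posture she has chosen for the music, then take the baseline heart rate and blood pressure together with the baseline 0-10 and STAI ratings. This keeps physiology and anxiety on the same baseline. Alternatively, leave the eligibility score where it is and move only the vital signs. State which in advance, because the 0-10 score also decides eligibility.
2. Take the immediate post-music reading in that same posture.
3. Record posture at all four readings.
4. In I.1, name baseline to immediate post-music as the main physiologic comparison. Report the transport and OR readings with posture noted.

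The woman's choice of position is unchanged. The cost is a minute or two of settling and one extra form field. If only the vital signs move, the anxiety ratings and vital signs no longer share a time point. In either case the result remains an uncontrolled pre/post comparison that carries time and waiting effects, and it should be reported as such.

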1. *Describe the criteria that define who will be excluded in the study as a numbered list:*
 1. Patient refusal.
 2. Impaired hearing.
 3. Patient is taking at least one anxiolytic medication daily at baseline.
 4. No anxiety (a score of 0, on a scale of 0-10 of pre-music exposure anxiety) after consent is given.
 5. ASA physical status rating of IV or higher. (Incapacitating disease that is a constant threat to life; a moribund patient who is not expected to live 24 hours with or without surgery)
 6. Severe medical condition(s) of the fetus or other pregnancy complications (ex: congenital heart defects, physical malformations, pre-term delivery, etc.)
2. *Describe in detail how the eligibility criteria will be assessed and satisfied (e.g., medical record review, physical examination):*
A brief medical record review, discussion with the patient, and pre-music anxiety assessment (after consent is given) will be performed.
3. *State who will determine eligibility. Note that those who are designated to determine eligibility must have appropriate training, expertise, and oversight, for example a physician PI or Co-I on a biomedical study:*
Either the PI or Co-investigator will determine final eligibility.
4. *Can study subjects participate in another research study while participating in this research study:*
 Yes No

D.3 Withdrawal of Subjects

1. *Describe anticipated circumstances under which subjects will be withdrawn from the research without their consent:*
Participants who score a 0 on their pre-music anxiety assessment will be withdrawn from the study.
2. *Describe procedures that will be followed when subjects withdraw voluntarily or are withdrawn from the research, including the possibility of partial withdrawal from study intervention with continued data collection:*
Participants who are withdrawn from the study will be provided the standard of care at Tufts Medical Center. All collected data and identifying information will be promptly destroyed.
3. *Describe any necessary safety precautions to be applied to subjects who withdraw or are withdrawn (tapering drug doses, evaluative x-ray, etc.):*
 N/A

D.4 Recruitment and Retention

D.4.1 Local Recruitment Methods

Describe the following attributes of the recruitment plan for the local Tufts site:

1. *When, where, and how potential subjects will be recruited:*
 - a. *Source of subjects (for example, patient population, local community, etc.):*

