6. *For Humanitarian Use Device (HUD) uses provide a description of the device, a summary of how you propose to use the device, including a description of any screening procedures, the HUD procedure, and any patient follow-up visits, tests or procedures* N/A

F.3 Evaluations

Will you perform any laboratory tests for this study?

Yes No

F.4 Collection, Storage, and Use of Human Biospecimens for Unspecified Future Research (formerly referred to as “Tissue Banking”)

Will biospecimens be collected and stored for unspecified future research?

Yes No

G. Ethics and Protection of Human Subjects

G.1 Informed Consent Process

Will subjects be required to provide informed consent?

Yes No

If Yes, respond to all of the following:

1. *Where the consent process will take place (e.g. a private clinic room):*
The informed consent will be taken in-person in the pre-op area in a private room.
2. *Anticipated amount of time a potential subject will have to make a decision about participation in the study:*
The patient is anticipated to decide within roughly 15 minutes. However, this is not a cutoff and it will be ensured that patients will not be coerced and will be given ample time to think about enrollment.
3. *Processes to ensure ongoing consent throughout the study:*
The researcher will be present for the entirety of the study intervention and will be able to stop the intervention at any point if the patient wishes to discontinue their involvement. Patients will also be informed that they are able to withdraw from the study at any time.
4. *Role of each research team member involved in the informed consent process (Please note, in general, for studies designated by the IRB as greater than minimal risk, a physician PI or Co-I must perform the informed consent process with subjects. A study coordinator/clinical research associate may not consent subjects. A study coordinator/clinical research associate may assist with this process; however, the PI or Co-I should be present to discuss the study with the subject and answer questions, and the PI or Co-I should sign the ICF documenting that s/he has performed the informed consent process with the subject and the subject understands the study.):*
Either the PI or Co-I will perform the consent process.
5. *Check to confirm you will follow “[SOP: Informed Consent Process for Research \(HRP-090\)](#)”.*

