For the purposes of this study, the principal investigator will periodically evaluate the safety data and assess the risks and benefits to assess subject safety.
 - c. *How the safety information will be obtained and documented (e.g., case report forms, by telephone calls with participants, printouts of laboratory results, etc.):*
The standard of care at Tufts Medical Center is to collect safety information on all patients undergoing surgery through an established computerized system called Anesthesia Touch. This study will also utilize this system to monitor research safety information.
 - d. *The frequency of data collection, including when safety data collection starts:*
Information will be obtained after subject consent with frequency of data collection aligning with the standard of care at Tufts Medical Center.
 - e. *The frequency or periodicity of review of cumulative data:*
Standard safety data review intervals per Tufts Medical Center protocols.
 - f. *The statistical tests for analyzing the safety data to determine whether harm is occurring:*
The statistical tests that will be performed on the safety data to determine whether harm is occurring will include a chi-squared test, to compare proportions between groups.
 - g. *Any conditions that trigger an immediate suspension of the research or other action for the research:*
In the unlikely event of serious patient harm or an unreasonable level of interference with the standard of care at Tufts Medical Center.

2. *Describe the entity responsible for monitoring the data, and their respective roles (e.g., the investigators, the research sponsor, a coordinating or statistical center, an independent medical monitor, a Data and Safety Monitoring Board (DSMB) /Data Monitoring Committee (DMC), and/or some other entity, and the timeframe for reporting events to this entity:*
As mentioned above, the principal investigator will periodically evaluate the safety data and assess the risks and benefits to assess subject safety.
3. *A copy of the DSMB/DMC Charter if the study is enclosed with the submission:* Yes N/A

G.7 Subject Populations & Vulnerable Populations

1. Can or will pregnant women be enrolled?

Yes No

If Yes, respond to all of the following:

- a. *Describe any preclinical studies, including studies on pregnant animals, and clinical studies, including studies on non-pregnant women, that have been conducted that provide data for assessing potential risks to pregnant women and fetuses:*

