- b. *Estimate the number of subjects needed to complete the study at the Tufts site:* 60 subjects

- c. *Provide the rationale for enrolling this number of subjects at the Tufts site:*

As mentioned above, previous sequential allocation biased coin design studies suggest that 20-40 subjects are required for adequate statistical power.

- d. *If a large number of withdrawals and/or dropouts is expected, explain why:*

Withdrawal/dropout rate is expected to be roughly 10%.

I.4 Data Management

1. *Describe the data analysis plan, including descriptions of the data:*

Data collection forms and an excel spreadsheet with all the analyzed data will be stored during the study period in the PI's private locked office and/or cloud account, where access is exclusive to the research team.

2. *Describe the steps that will be taken to secure the data (e.g., training, authorization of access, password protection, encryption, physical controls, certificates of confidentiality, and separation of identifiers and data) during storage, use, and transmission:*

As mentioned above, physical data will remain in a locked private office to which access is restricted to research team members only. To separate and distinguish ICFs between this study and the previous, similar study (IRB STUDY #00001496), the physical forms will be kept in a folder/binder of a different color with clear labels. All electronic data will be held in a password protected, encrypted account within Tufts CTSI REDCap. Data will be coded. Each participant will be assigned a unique randomly generated three-digit number that will be linked with their medical record number on the key. Duplicates will be

¹ ¹ If Tufts IRB is requested to be the Single IRB of Record for external sites (as per section **Error! Reference source not found.**), include all sites in these enrollment numbers.

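### The chi-squared test named to detect harm compares two music arms, so it addresses only harm that differs by music type, and no pooled harm estimate is named

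*Combined protocol and SAP*

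**What the plan says.** Section G.6 item 1a of the combined protocol and SAP lists the safety events to be collected: agitation, and ear injury or hearing problems. Item 1f then gives the statistical method. The tests "to determine whether harm is occurring will include a chi-squared test, to compare proportions between groups". No second test or estimate follows.

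The groups are fixed elsewhere. F.2 has every participant who enters the intervention listen to music: "The study subjects will listen to this music played from a speaker connected to an audio device". I.1 sets the between-arm efficacy comparison "between the Mozart and personal-preference intervention arms", and I.5 randomises to these two groups in equal ratio. No group without music is randomised or sized. I.2 plans up to 33 per group, with a minimum of 30.

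The statistical section adds no harm analysis. I.1 item 2 marks safety endpoints as not applicable, and I.2 item 1 covers only the ED95. One secondary endpoint is to "analyze and compare pre-and post-intervention heart rate and blood pressure measurements", which does not count agitation or ear and hearing events.

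Two passages bear on who would be counted. Under G.1 item 3 the researcher "will be able to stop the intervention at any point if the patient wishes to discontinue their involvement". D.3 item 2 says of withdrawn participants: "All collected data and identifying information will be promptly destroyed".

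**The concern.** Item 1f is meant to say how the study will tell whether harm is occurring. A comparison of two arms that both receive the intervention can speak only to a difference between them. If music, or the study procedure around it, upset participants equally in both arms, the test would be expected to show nothing.

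What is at stake is interpretation. With this test as the only named harm analysis, a non-significant p-value could be reported as reassurance, although it says nothing about how many participants had an event. Per-arm counts will exist, because the test needs them. What is not planned is a pooled proportion with an interval, which would tell a reader how large a harm rate the data leave open.

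**Working it through.** **Inputs from the documents.** Two music arms in equal ratio (I.5); 33 enrolled and at least 30 completing per arm, with about 10% attrition (I.2). The plan's own figure is consistent: 33 × 0.9 = 29.7, about 30 per arm, so 60 in all.

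**Assumptions.** The documents give no event rate, significance level or continuity correction for the safety test. I use two-sided 0.05, a range of event rates, and the test both without and with the Yates correction.

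**Step 1: the statistic.** With a and b events among n per arm, the uncorrected statistic is X² = 2n(a − b)² / [(a + b)(2n − a − b)]. With Yates, |a − b| is replaced by |a − b| − 1. It depends on the gap between arms. For a = b = 6 and n = 30, a − b = 0, so X² = 0 and p = 1, while 12/60 = 20% had an event.

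**Step 2: equal harm in both arms.** The rejection probability is the sum of Bin(a; n, p) × Bin(b; n, p) over all tables with X² above 3.84.

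| Common event rate | n = 30, uncorrected | n = 30, Yates | n = 33, uncorrected | n = 33, Yates |
|---|---|---|---|---|
| 5% | 0.028 | 0.002 | 0.033 | 0.002 |
| 10% | 0.054 | 0.009 | 0.057 | 0.012 |
| 20% | 0.049 | 0.022 | 0.052 | 0.024 |
| 50% | 0.052 | 0.027 | 0.064 | 0.036 |

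Rejection stays near or below the nominal level even when half of all participants have an event. This is how a valid test behaves under its null hypothesis, and it shows that common harm is that null.

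**Step 3: differential harm.** Against 0/30 in one arm, the smallest significant count in the other is:
- 4/30 uncorrected: X² = 60 × 16 / (4 × 56) = 4.29 (3/30 gives 60 × 9 / (3 × 57) = 3.16)
- 6/30 with Yates: X² = 60 × 25 / (6 × 54) = 4.63 (5/30 gives 60 × 16 / (5 × 55) = 3.49)

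For assumed true rates of 5% and 15%, power at 30 per arm is 0.26 uncorrected and 0.09 with Yates. The test does address differential harm, but weakly at a contrast of this size.

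**Step 4: what a pooled estimate would show.** The Clopper-Pearson 95% limits for x events in N are the Beta(x, N − x + 1) quantile at 0.025 and the Beta(x + 1, N − x) quantile at 0.975. For x = 0 the upper limit is 1 − 0.025^(1/N).

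| Events / exposed | Proportion | Exact 95% CI |
|---|---|---|
| 0/30 (one arm) | 0% | 0 to 11.6% |
| 0/60 | 0% | 0 to 6.0% |
| 6/60 | 10% | 3.8% to 20.5% |
| 12/60 | 20% | 10.8% to 32.3% |

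The last row is the same data as 6/30 against 6/30 in step 1.

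**The case against.** The strongest reply is that little is missing. The wording of item 1f leaves the list of tests open, and the pooled count follows by adding the two arms. H.1 anticipates no physical risk. Common harm is also watched case by case: under H.2 the co-investigator monitors for ear injury and agitation, passes events to the principal investigator, and reports go to the department within 24 hours. G.6 adds periodic review by the principal investigator and a condition for suspending the study. None of this needs a chi-squared test. All of it stands, and it limits the weight of the point. It does not supply a rate or an interval, and item 1f is where the plan states its statistical method.

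A second reply is that a pooled rate does not show that music caused anything. This also stands. Without a no-music arm the rate mixes music-related agitation with the agitation expected before surgery. The gain is a harm summary that can be interpreted, not attribution.

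A reader might infer that participants who withdraw because of agitation disappear from the safety data. The documents do not establish this. The destruction sentence in D.3 item 2 speaks of participants who are withdrawn, and the only circumstance listed in item 1 is a zero baseline score, which occurs before any music. The prompt for item 2 covers voluntary withdrawal as well, so the wider reading is possible but not the only one. Safety information is also captured in the anaesthesia record system (G.6 item 1c), and H.2 describes entries in the medical record and a departmental Quality Assurance form. Nothing says that those records are destroyed. What remains is an ambiguity that a tally of withdrawals would expose.

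**Conclusion.** The point holds, and it is minor. The one named harm analysis addresses only harm that differs by music type. Harm common to both arms is its null hypothesis, and no pooled harm estimate is named elsewhere. The reasoning rests on the design alone. The rejection rates and power rest on the assumed significance level and event rates, and the intervals on the assumed counts and 30 participants per arm.

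Two stronger conclusions might be drawn, and the documents support neither. One is that the test cannot detect harm at all: harm specific to one type of music is harm, and the test does address it, with limited power. The other is that participants' safety depends on this test: the case-level safeguards in G.6 and H.2 operate without it. No efficacy result changes.

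**What to change.** In G.6 item 1f:

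- Make the main harm summary the count and proportion of participants with each collected event (agitation; ear injury or hearing problems), per arm and pooled over all participants exposed to music, with exact Clopper-Pearson 95% intervals.
- Keep the chi-squared test as a secondary comparison, described as addressing differential harm only.
- State that a non-significant result is not evidence of no harm.
- State that, without a no-music arm, the pooled rate is descriptive and cannot separate music-related from background pre-operative agitation.
- Report the number of exposed participants who withdraw, per arm, because D.3 can be read as destroying their study data.

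The cost is a few sentences and a simple tally, submitted as an ordinary amendment. It needs no extra participants and no new measurements.
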